Investigational Device	Nerivio [™] is an FDA-authorized remote electrical neuromodulation (REN) device for the acute treatment of migraine with or without aura in patients 18 years old or above who do not have chronic migraine. The device delivers transcutaneous electrical stimulation to the upper arm to induce conditioned pain modulation (CPM) that activates a descending endogenous analgesic mechanism. The electrical stimulation generated by the device is similar to other FDA approved electrostimulation devices. The treatment is self-administered and controlled by a smartphone application. A recent pivotal study in adults demonstrated that the device provides an effective acute migraine treatment with a favorable safety and tolerability profile.		
Objectives	To evaluate the safety and efficacy of Nerivio™ in the acute treatment of migraine in adolescents (12 to 17 years of age).		
Participant Population	Adolescents 12-17 years old meeting the International Headache Society criteria (ICHD-3) for migraine with or without aura, with a least 3- migraine attacks per month.		
Sample size	Up to 130 participants		
Inclusion Criteria	 Participants age 12-17 years old at the time of informed consent, inclusive. Participants have at least a 6-month history of headaches that meet the ICHD-3 diagnostic criteria for migraine with or without aura History of at least 3 migraine attacks per month for each of the 2 months preceding study enrolment Typical headache duration of at least 3 hours (when untreated or unsuccessfully treatment) Stable migraine preventive medications during the 2 months prior to enrollment (no change in usage or dosage). Participants have personal access to a smartphone (24/7) Participants must be able and willing to comply with the protocol Parents/Guardians must be able and willing to provide written informed consent Participants must be able and willing to provide informed assent 		
EXCIUSION CINERIA	 Participants with an implanted electrical and/or neurostimulator device (e.g. cardiac pacemaker, cochlear implant). Participants with congestive heart failure (CHF), severe cardiac or cerebrovascular disease. Participants with epilepsy. Medical use of cannabis or recreational use one month prior to enrollment. Participants who have undergone nerve block (occipital or other) in the head or neck within the last 2 weeks Treatment with onabotulinum toxin A (Botox) to the head and/or neck for 3 months before enrollment and/or during the study Any history of anti-CGRP antibody treatment Current participation in any other clinical study that includes treatment Participants without basic cognitive and motor skills required for operating a smartphone. 		

Nerivio TCH-004 Clinical Study Protocol (NCT04089761)

Doc ID: TEC0105

Revision #: 1.0 Page: 9 of 49

	40. Drawaget an horsette a dia n familie			
	10. Pregnant or breastfeeding females			
	11. Pure menstrual migraine 12. Participants who received parenteral treatments for migraine within the			
	previous 2 weeks.			
	13. Participants with other significant pain, medical or psychological problems			
	that in the opinion of the investigator may confound the study assessments			
	14. Participants who have previous experience with the device			
	15. Participants with arm circumference below 7.9 inches (20 cm)			
Study Design	A prospective, single arm, open label, multicenter trial.			
ctualy 2001g.	The study will be conducted in three phases:			
	Phase I - Run-in:			
	Eligible participants will be trained to use a smartphone migraine diary			
	application for 4 weeks. Participants who report at least 3 migraine attacks			
	with at least 3 hours duration (if not treated or if unsuccessfully treated), will			
	be included in the treatment phase.			
	Phase II - Treatment phase:			
	Participants who meet the run-in requirements will receive an active Nerivio			
	device. Participants will be instructed to use the device for the treatment of 4			
	qualifying migraine attacks (see below) within 60 minutes of onset during a			
	period of up to 8-week. The participants will use the app to record pain intensity			
	levels at baseline, 2- and 24-hours post-treatment, and to record the			
	presence/absence of associated migraine symptoms (nausea, photophobia,			
	phonophobia) at baseline and 2 hours post-treatment. The first reported			
	treatment will be considered a "training" treatment, aimed to verify the			
	participants use the device properly, and will only be included in the safety			
	analysis. The first treatment of a qualifying attack after the training treatment is considered a test treatment and will be used for all efficacy analyses. The			
	is considered a test treatment and will be used for all efficacy analyses. The			
	efficacy endpoints will be assessed on evaluable treatments of qualifying			
	attacks.			
	Phase III (optional) - Free-use: Participants who complete the treatment phase will be offered the opportunity			
	to participate in an 8-week free-use phase in which they will be able to			
	incorporate the Nerivio device into their usual care.			
Qualifying migraine	A qualifying migraine attack is defined as a migraine attack that:			
attack	was not preceded by another migraine attack or other headache			
attack	within the preceding 24 hours			
	was not preceded by the use of specific or non-specific acute			
	migraine medications within the previous 24 hours			
	3. occurred in a setting in which the patient could properly administer			
	the treatment (that is, it is possible to initiate a complete treatment			
	within 60 minutes of onset and the participant will be able to			
	complete the migraine diary at 2 hours after treatment)			
Primary endpoints	1. The safety of Nerivio			
i innary enuponits	The incidence of adverse events in general and by seriousness, severity			
	and association to the device.			
	2. Treatment tolerability			
	The percent of subjects who fail to complete the study because of adverse			
	events			
Secondary endpoint	Pain relief at 2 hours post-treatment:			
Occomulary emuporing	The proportion of participants achieving pain relief at 2 hours post-			
	treatment in the test treatment, with no use of rescue medication			
	2. Pain-free at 2 hours post-treatment:			
	2. I dill 1100 dt 2 110d13 post-trodutiont.			

Nerivio TCH-004 Clinical Study Protocol (NCT04089761)

Doc ID: TEC0105

Revision #: 1.0 Page: 10 of 49

	The proportion of participants achieving pain freedom at 2 hours post-			
	treatment in the test treatment, with no use of rescue medication			
	3. Disappearance of associated symptoms at 2 hours post-treatment			
	Disappearance of nausea in the test treatment at 2 hours post-treatment			
	II. Disappearance of phonophobia in the test treatment at 2 hours post-treatment			
	III. Disappearance of photophobia in the test treatment at 2 hours post-treatment			
Exploratory	Sustained pain relief at 24 hours post-treatment:			
endpoints	The proportion of participants achieving pain relief at 2 hours post-			
	treatment in the test treatment, with no use of rescue medication and no			
	relapse of headache pain within 24 hours			
	2. Sustained pain-free at 24 hours post-treatment:			
	The proportion of participants achieving pain freedom at 2 hours post-			
	treatment in the test treatment, with no use of rescue medication and no			
	relapse of headache pain within 24 hours			
	Functional disability at 2 hours post-treatment			
	The proportion of participants achieving improvement of at least one			
	grade in functional disability in the test treatment at 2 hours post-			
	treatment with no use of rescue medication			
	Functional disability at 24 hours post-treatment			
	The proportion of participants achieving improvement of at least one			
	grade in functional disability in the test treatment at 24 hours post-			
	treatment with no use of rescue medication			
Datasets	Intent to treat analysis set (ITT)			
	The ITT analysis set includes all participants undergoing the treatment			
	phase.			
	Modified intent to treat analysis set (mITT)			
	The mITT analysis set includes all participants undergoing the			
	treatment phase who treat a test treatment within 60 minutes of attack			
	onset.			
Data Analysis	The ITT analysis set will be used for the primary endpoints of safety and			
	tolerability assessments. Safety assessments will include spontaneously			
	reported adverse events. The mITT analysis set will be used for the efficacy			
	assessments.			

Nerivio TCH-004 Clinical Study Protocol (NCT04089761)

Doc ID: TEC0105

Revision #: 1.0

Page: 11 of 49

2. Background

Migraine is one of the most prevalent and disabling neurologic disorders [1], characterized by recurrent headache attacks with nausea, vomiting, photophobia, and phonophobia [2]. Migraine is also common in adolescents (12 to 17 years of age) [3]. Migraine in adolescents has also been associated with disability as evidenced by missed school days [4], poorer performance in school [5] and a negative impact on quality of life [6].

The majority of current migraine acute treatments for adolescents are pharmacological [7]. Not all adolescents find these to be effective, they can cause side effects, and their overuse may lead to medication overuse headache [8,9] and migraine chronification [10]. According to the American Academy of Neurology (AAN) and Child Neurology Society (CNS) evidence-based guidelines, ibuprofen, acetaminophen and sumatriptan nasal spray should be considered for the acute treatment of migraine in adolescents, but there is no supporting data for the use of oral triptans in adolescents [11]. Thus, there is a great unmet need for alternative acute migraine treatments that are both effective and well tolerated. Such developments hold the potential to improve the health and quality of life of youth with migraines.

Non-invasive neuromodulation is safe, well-tolerated, and may have fewer adverse effects than drugs [12,13]. However, the efficacy of current neuromodulation devices approved for migraine acute treatment in adults (above the age of 18 years) has not been established in adolescents. Thus, new non-pharmacological alternative acute migraine treatments are needed. Remote electrical neuromodulation (REN) [14] is a novel acute migraine treatment which stimulates upper arm peripheral nerves to induce conditioned pain modulation (CPM) - an endogenous analgesia mechanism in which conditioning stimulation inhibits pain in remote body regions [15].

The safety and efficacy of REN (Nerivio[™], Theranica Bio-Electronics LTD., Israel) has been recently assessed in adults in a randomized, double-blind, sham-controlled multicenter study (NCT03361423). This study demonstrated that REN provides superior clinically meaningful relief of migraine pain and MBS compared to placebo, offering a safe and effective non-pharmacological alternative for acute migraine treatment. Specifically, the active stimulation was more effective than sham stimulation in achieving pain relief (66·7% [66/99; Cl_{95%} 56·48-75·82] vs. 38·8%, p<0·001), pain-free (37·4% vs. 18·4%, p<0·005) and MBS relief (46·3% vs. 22·2%, p<0·001) at 2 hours post-treatment, and that the pain relief and pain-free superiority of the active treatment was sustained 48 hours post-treatment. In addition, the incidence of device-related adverse events was low and similar between treatment groups (4·8% vs. 2·4%, p=0·49). All device-related adverse events were mild, did not required medical intervention and resolved within 24 hours. The device was granted a 510k De novo approval (DEN180059)

Nerivio TCH-004 Clinical Study Protocol (NCT04089761)

Doc ID: TEC0105 Revision #: 1.0

Page: 12 of 49

The aim of the present study is to evaluate the safety and efficacy of REN for the acute treatment of migraine in adolescents.

3. Identification and description of the device information

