The individual intensity level identified during this visit will be recorded, and the participants will be asked to treat their migraine headaches with the device using the identified intensity. If the research staff recognizes that the participant cannot tolerate the feeling of the electrical stimulation, the participant may be withdrawn from the study.

During the training, participants will also be informed on the key elements which are critical for the successful conduct of the study:

- Treatments of attacks with Nerivio[™] should be performed as soon as possible
 after migraine headache or aura began and always within one hour of symptoms
 onset. Treatments of mild headaches are accepted.
- Avoid taking rescue medications within two hours post-treatment (2 hours from start of treatment), if possible.
- The treatment should be performed for at least 30 minutes (the recommended treatment duration is 45 minutes).

Phase 2 –Treatment phase: Participants will be instructed to use the device for the treatment of 4 qualifying migraine attacks (see below) as soon as possible and always within 60 minutes of onset during a period of up to 8 weeks. Participants will be instructed to use the device with the intensity level identified during the device training visit (with a range of ±5 units) and make sure the stimulation is perceptible but not painful. Participants will be instructed to avoid taking rescue medications within 2 hours post-treatment. If medications are used, participants will be instructed to record in the app when and which medication was taken. The participants will use the app to record pain intensity levels (none, mild, moderate, or severe) at baseline, 2- and 24-hours post-treatment, and to record the presence/absence of associated migraine symptoms (nausea, photophobia,

Nerivio TCH-004 Clinical Study Protocol (NCT04089761)

Doc ID: TEC0105

Revision #: 1.0

Page: 30 of 49

phonophobia) at baseline and 2 hours post-treatment. To assess functional disability, participants will also record at baseline, 2- and 24-hours post-treatment their response to the following question in their diary: "How do you rate your ability to do school-work or perform your usual activities?" using a 4-point scale ('as usual', 'some ability', 'a little ability', 'no ability at all'). At the beginning of each treatment, participants will also be asked to report the time elapsed from attack onset. Adverse events will be reported throughout this phase of the study.

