Participants who do not achieve satisfactory relief at 2 hours post-treatment may treat again with the Nerivio[™] device or may treat with usual care at that time or any time thereafter if the headache does not resolve. Participants will also be able to treat headache recurrence with the device. Attacks that are not treated with the device may be treated with usual care.

The first reported treatment will be considered a "training" treatment, aimed to verify that the participants use the device properly, and will only be included in the safety analysis. The efficacy evaluation will be performed on the first treatment of a qualifying attack (see below) following the training treatment (hereby termed "test treatment").

Qualifying migraine attack

A qualifying migraine attack is defined as a migraine attack that:

- 1. Was not preceded by another migraine or other headache within the preceding 24 hours
- 2. Was not preceded by the use of specific or non-specific acute migraine medications within the previous 24 hours
- Occurred in a setting in which the patient could properly administer the treatment (that is, it is possible to initiate a complete treatment within 60 minutes of onset and the participant will be able to complete the migraine diary at 2 hours after treatment)

Third visit – Termination of the treatment phase and free-use phase initiation: Following the 8-week period of the treatment phase, participants will return to the clinic to return the device and fill questionnaires assessing satisfaction and user experience. All participants who complete the treatment phase will be offered to participate in an additional 8-week phase in which the device can be incorporate into usual care.

Phase 3 – Free-use phase: Participants will continue in an 8-week phase in which they will be able to use the device according to their preferences for the treatment of their migraine attacks.

Fourth (final) visit – End of study: Participants will return to the clinic following the end of the 8-week free-use phase, at which time they will return the device.

Nerivio TCH-004 Clinical Study Protocol (NCT04089761)

Doc ID: TEC0105

Revision #: 1.0 Page: 31 of 49

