6.4. Study endpoints

6.4.1. Primary endpoints

1. The safety of Nerivio

The incidence of adverse events in general and by seriousness, severity and association to the device.

2. Treatment tolerability

The percent of subjects who fail to complete the study because of adverse events

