6.6. Data management

The data management function will be supported by a cloud-based electronic data capture (EDC) system developed by FlaskData.IO (Modi'in, Israel). FlaskData.IO provides services for collection and remote monitoring of clinical trials data, compliant with HIPAA and 21 CFR Part 11. EDC portals with secure authorized access will be made available to every participating site, as well as to the study monitor.

Data captured by the clinical personnel will be entered directly into pre-specified eCRF screens by the site personnel. Data from paper sources will be entered into the study database. Automatic data checks will be implemented for majority of entry fields to provide opportunity for resolving data inconsistencies as soon as possible to its occurrence. Efforts will be made to identify missing or incorrect data and promptly resolve these issues.

Data collected by the smartphone application will be directed to a secured cloud-based database where it will undergo analysis aimed at detecting of missing data and other inconsistencies. The smartphone will transmit PRO and technical data containing activation times, stimulation intensity and ePRO via the smartphone to a central electronic database for analysis. Activities such as repeatedly aborted programs, missing feedbacks, inconsistent stimulation intensity adjustments, will be communicated to the research coordinator of the corresponding site, using the participants' ID codes. Automated means were developed to identify and provide corresponding notifications regarding events that

Nerivio TCH-004 Clinical Study Protocol (NCT04089761)

Doc ID: TEC0105

Revision #: 1.0

Page: 33 of 49

may lead to protocol deviations and/or missing data, and which resolution may require involvement of study personnel. Examples of such events include missing PRO data or low device battery level. An automated system was implemented to notify the participant, site study coordinator and the sponsor's study monitor of such issues. Missing data will be automatically identified by a script running on the cloud of FlaskData.IO, and queries will be generated to the participants and the corresponding site study coordinator. Near real time detection of problems in accumulating data will allow timely generation and resolution of queries. Intermediate data processing and translation into eCRF format will be performed. Processed data are further pushed into the EDC system.

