12.3. Anticipated device-related AEs

Possible adverse events associated with remote electrical neuromodulation include, but are not limited to, the following:

- Numbness of the hand/arm
- Itching
- Muscle spasms
- Redness
- Warmth sensation
- Tingling
- Pain in the arm

All anticipated devoice-related AEs, if present, are temporary and should disappear shortly after the treatment.

The following migraine symptoms are foreseeable and will not be considered as device related: headache, nausea, light sensitivity, sensitivity to noise, allodynia, abdominal pain,

Nerivio TCH-004 Clinical Study Protocol (NCT04089761)

Doc ID: TEC0105

Revision #: 1.0

Page: 45 of 49

loss of appetite, cold or heat sensation, paleness, fatigue, dizziness, anxious mood, fever (rare), blurred vision, vision symptoms such as bright flashing dots or lights, blind spots, wavy or jagged lines (aura).

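### Adverse-event incidence is the first primary endpoint, but the protocol names only spontaneous reporting and no question, channel or timing, so short-lived device effects are at risk of being under-counted

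*Combined protocol and SAP*

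**What the plan says.** Section 6.4.1 defines primary endpoint 1 as "The incidence of adverse events in general and by seriousness, severity and association to the device". Primary endpoint 2 is "The percent of subjects who fail to complete the study because of adverse events". Section 7.2.1 adds an analysis of time to resolution, and 12.1 asks for durations below one day to be recorded in suitable units.

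On collection, the Synopsis (Data Analysis) states "Safety assessments will include spontaneously" reported adverse events. Section 6.3, treatment phase, states "Adverse events will be reported throughout this phase of the study". Section 12.2 covers entry on the AE form, optional visits to monitor an event, and follow-up of an ongoing device-related event. It does not say when or how the participant is asked.

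The diary, by contrast, is set out closely: "The participants will use the app to record pain intensity levels (none, mild, moderate, or severe) at baseline, 2- and 24-hours post-treatment", followed by associated symptoms, a worded functional-disability question, time since onset and any medication taken. Section 6.6 describes the data stream: "The smartphone will transmit PRO and technical data containing activation times, stimulation intensity and ePRO". At Visit 3 participants "return the device and fill questionnaires assessing satisfaction and user experience"; the task listed for Visit 4 is device return.

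Section 12.3 says of the expected device effects: "All anticipated devoice-related AEs, if present, are temporary and should disappear shortly after the treatment". In the adult pivotal study (4.2.2) all device-related events resolved within 24 hours.

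**The concern.** An event that lasts minutes or hours during unsupervised home use enters the data only if the participant raises it or someone asks. The protocol describes no routine asking. If a 12- to 17-year-old does not volunteer a brief warmth or numbness, the next scheduled contact that could bring it out is up to 8 weeks away.

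Missed events would lower the primary incidence, which favours the device. In a randomized trial, similar under-capture in both arms would at least leave a comparison. Here the absolute rate is the result, and nothing in the analysis would signal a shortfall: a confidence interval reflects sampling error, not incomplete capture. Resolution times are exposed in the same way for any event first mentioned at a visit.

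**Working it through.** **1. What is specified and what is not**

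| Element | Pain, symptoms, function | Adverse events |
|---|---|---|
| Question or item | Given (6.3) | Not given |
| Timing | Baseline, 2 h and, for pain and function, 24 h | Throughout the treatment phase |
| Channel | App | Not given; AE form for recording (12.2) |
| Automated alerts (6.6) | Missing PRO data | None named |
| Visits 3 and 4 | Satisfaction and user-experience questionnaires (Visit 3) | No enquiry listed |
| Free-use phase | – | No capture described |

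The text supports the statement that no solicited AE question is specified. It does not support the statement that none exists.

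**2. Inputs for an illustration**

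The plan states no figure for AE capture, so there is none to reproduce. The inputs are:

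- N = 130, the maximum in 7.3.
- Adult device-related rate, active arm (4.2.2): 6/126 = 4.8%, exact 95% CI 1.8–10.1%.
- An alternative true rate of 10%. This is an assumption with no source in the documents.
- Capture fraction c of 100%, 70%, 60% or 50%. These are also assumptions.

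Expected recorded cases = N × p × c. The number recorded is taken as Binomial(N, p × c). Intervals are Clopper–Pearson. Section 7.5.4 prescribes exact 95% intervals for efficacy; for other results 7.5.1 asks for two-sided 95% intervals where appropriate.

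**3. True rate 4.8%**

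- Full capture: 130 × 0.0476 = 6.2 cases.
- 70% capture: 6.2 × 0.7 = 4.3 cases.
- 50% capture: 6.2 × 0.5 = 3.1 cases.
- Exact CI for 4/130: 0.8–7.7%. For 3/130: 0.5–6.6%. Both contain 4.8%.

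**4. True rate 10% (assumed)**

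- Full capture: 130 × 0.10 = 13 cases. At 70%: 9.1. At 50%: 6.5.
- Upper exact limits: 6/130 gives 9.8%, 7/130 gives 10.8%, 8/130 gives 11.8%, 9/130 gives 12.7%.
- The upper limit is therefore below 10% only when 6 or fewer cases are recorded.

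| Capture | Recorded rate p × c | P(6 or fewer of 130) |
|---|---|---|
| 100% | 10% | 2% |
| 70% | 7% | 19% |
| 60% | 6% | 33% |
| 50% | 5% | 52% |

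The bias has a known direction. Its size depends entirely on c, which the documents do not give.

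**The case against.** The strongest reply is that silence is not absence. The Synopsis says safety assessments include spontaneous reports, not that they consist only of them. Section 6.3 has AEs reported throughout the treatment phase, directly after the diary items, so contemporaneous reporting is contemplated. Section 9.1 lists the case report forms as separate documents, and they may hold an AE question. Intensity is set with staff at Visit 2, so effects at that session can be observed, and 12.2 allows extra visits to follow an event. Repeated prompts also have a price: they will draw in migraine symptoms that 12.3 says are not device-related.

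Most of this stands, and it rules out two stronger readings. A reader might infer that the diary has no AE item and that events are under-counted; the documents show neither. A reader might also infer that the interval would exclude the true rate; at an assumed 10% that holds for 6/130 but not for 7 to 9/130, and at the adult rate the intervals at the expected counts contain the truth.

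The reply does not close the gap. Section 9.1 lets the case report forms change without a protocol amendment, so ascertainment of a primary endpoint would rest on a document outside the protocol. Staff presence at Visit 2 does not cover home use. Extra visits under 12.2 follow events already known. The migraine-symptom objection is met by tabulating prompted and volunteered events separately.

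**Conclusion.** The concern holds as a risk, not as a demonstrated under-count. The protocol names spontaneous reporting as its only method for its first primary endpoint and specifies no question, channel or timing. With brief effects and 8-week visit gaps, any loss lowers the recorded rate, and a single-arm design cannot show that this has happened.

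The size cannot be estimated from the documents. The figures above rest on assumed capture fractions and, for the 10% case, on an assumed true rate. They range from a loss of about 2–3 of 6 expected cases, with intervals that still cover the truth, to about an even chance that the upper limit misses a true 10%. The adult 4.8% serves only as a reference value: the documents do not say how that study collected events, so comparability should not be claimed. The protocol should be changed, but nothing here shows the safety result to be invalid.

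**What to change.** In 6.3, add one non-leading yes/no item to the 2-hour and 24-hour app prompts, for example: Did you notice anything unusual or unpleasant since starting the treatment? Route any yes to the site for physician assessment under 12.1. Ask the same open question at Visits 3 and 4, so that the free-use phase is covered too. If the app or case report form already has such an item, state its wording and timing in the protocol instead.

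In 7.5.3, report AE incidence overall and separately for prompted and volunteered events.

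The cost is one diary item and site follow-up of positive answers. The recorded AE rate will probably be higher, and some migraine symptoms will be reported as events. The relatedness rules in 12.1 and 12.3 already deal with these. One entry needs care: 12.3 lists heat sensation as a migraine symptom and warmth as a device effect, so the site record should note where it was felt. No treatment or clinical rule changes.
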